### 8.10 Pharmacokinetic Blood Sample Collection and Processing

Whole blood samples for pharmacokinetic (PK) analysis of nintedanib levels will be collected via venipuncture. This will only be performed on the first 32 patients enrolled in the study.

Samples for pharmacokinetic analysis (PK) of nintedanib levels will be collected using 1, 10 mL purple EDTA collection tube.

Pharmacokinetic sample (PK) collection will be obtained on:

- Cycle 1/Day 1 – Pre-dosing: PK
- Cycle 1/Day 1 – 0.5-1 hr post-dosing: PK
- Cycle 1/Day 1 – 2-4 hr post-dosing: PK
- Cycle 1/Day 1 – 5-6 hr post-dosing: PK
- Cycle 1/Day 1 – 7-8 hr post-dosing: PK
- Cycle 1/Day 2 – Pre-dosing: PK
- Cycle 1/Day 15 – Pre-dosing: PK
- Cycle 1/Day 15 – 2-4 hr post-dosing: PK
- Cycle 1/Day 15 – 5-6 hr post-dosing: PK

**Note:** All dosing dates and times must be recorded on the study medication diary **and** in the eCRF for all doses taken from the first dose to the day of the last PK sample.

**NOTE:** *Any samples that have been hemolyzed should be re-drawn if possible.*

Nintedanib is degraded by plasma esterases; therefore, whole blood samples should be immediately maintained in an ice bath until centrifuged. Centrifugation for separation of plasma should be done **within 60 min** after sampling:

- Centrifuge whole blood samples as soon as possible at 4°C using a refrigerated centrifuge at approximately 3000 rpm for about 10 min.
- Transfer at least 500 µL of the supernatant plasma into polypropylene vials (e.g., Nunc cryo-tubes, 1.8 mL).

**NOTE:** *Strictly avoid contamination with erythrocytes: If this occurs, the specimen must be centrifuged again.*

Plasma will be aliquoted into 2 cryovials per time-point. The screw cap polypropylene cryogenic tube will be labeled with the participant's MR number, (for RPCI participants) participant's initials, participant's study number, clinical study number, protocol time point, dose, and protocol day. The samples will immediately be frozen at - 70°C or below until analyzed.

Samples collected at RPCI will be processed and stored at RPCI's Hematological Procurement Facility. Frozen samples will then be analyzed in RPCI's Bioanalytics, Metabolomics & Pharmacokinetic Core Facility:

Roswell Park Cancer Institute  
Bioanalytics, Metabolomics & Pharmacokinetic Core Facility  
[name]  
Regarding Study #: I 265514  
[name]  
[name]  
[[contact]](mailto:[contact])

**Note:** All laboratories housing research samples need to maintain current, study-specific **Temperature Logs** and **Sample Tracking and Shipping Logs**. The Principal Investigator/Laboratory Manager **must** ensure that the stated lab(s) have a process in place to document the receipt/processing/storage/shipping of study-related samples/specimens (**ICH 8.3.25**). This is required for both observational and interventional clinical studies collecting clinical samples.

**NETWORK SITES:** Follow directions above for sample collection and processing. The cryogenic tubes will be labeled with the Subject ID # (unique to Network patients), initials, the participant's study number, clinical study number, protocol time point, dose, and protocol day. Frozen samples will be shipped via Fed Express Overnight on dry ice with delivery on Mon-Fri. **NO SATURDAY DELIVERY. All samples should be shipped batched at the end of the study to the address below with shipping log:**

Roswell Park Cancer Institute  
Bioanalytics, Metabolomics & Pharmacokinetic Core Facility  
[name]  
Regarding Study #: I 265514  
[name]  
[name]  
[[contact]](mailto:[contact])

For additional information regarding the handling of pharmacokinetic samples please contact RPCI's Bioanalytics, Metabolomics & Pharmacokinetic Core Facility laboratory at [contact] (Tel) or [contact] (Fax).

### **8.11 Biomarker Blood Sample Collection and Processing**

Whole blood samples for biomarker analysis (CAF: Circulating Angiogenic Factors) will be collected via venipuncture. This will only be performed on the first 32 patients enrolled in the study.

Samples for **biomarker analysis** (CAF) will be collected using 1, 10 mL green-top heparinized collection tube and 1, 10 mL purple EDTA collection tube.

Biomarker sample (CAF) collection will be obtained on:

- Cycle 1/Day 1 – Pre-dosing: CAF

- Cycle 1/Day 1 – 2-4 hr post-dosing: CAF
- Cycle 1/Day 15 – 2-4 hr post-dosing: CAF
- Cycle 3/Day 1 – 2-4 hr post-dosing: CAF

Plasma will be separated from whole blood within 30 minutes following the extraction (collection tubes are to be centrifuged at 1000g for 10 min at room temperature). Plasma will be aliquoted into 3 cryovials (approximately 1 mL/cryovial) per time-point. The screw cap polypropylene cryogenic tube will be labeled with the participant's MR number,(for RPCI participants) participant's initials, participant's study number, clinical study number, protocol time point, dose, and protocol day. The samples will immediately be frozen at -70°C or below until analyzed. Samples collected at RPCI will be processed and stored at RPCI's Hematological Procurement Facility. Frozen CAF samples will then be analyzed in RPCI's Genitourinary Malignancies Laboratory by [name]:

Roswell Park Cancer Center  
Genitourinary Malignancies Laboratory  
[name]  
Attn: [name] – I 265514  
[name]  
[name]  
[contact]  
[contact]

[[contact]](mailto:[contact])

**Note:** All laboratories housing research samples need to maintain current, study-specific **Temperature Logs** and **Sample Tracking and Shipping Logs**. The Principal Investigator/Laboratory Manager **must** ensure that the stated lab(s) have a process in place to document the receipt/processing/storage/shipping of study-related samples/specimens (**ICH 8.3.25**). This is required for both observational and interventional clinical studies collecting clinical samples.

**NETWORK SITES:** Follow directions above for sample collection and processing. The cryogenic tubes will be labeled with the Subject ID # (unique to Network patients), initials, the participant's study number, clinical study number, protocol time point, dose, and protocol day. The samples will immediately be frozen at -70°C or below (samples are to be stored until requested for batch mailing). Samples are to be **batch shipped frozen at the end of study with shipping log, on dry ice**.

Frozen samples will be shipped via Fed Express Overnight on dry ice with delivery on Mon-Fri. **NO SATURDAY DELIVERY**. Do not ship on a Friday or the day before a holiday.

Address shipments and any questions regarding specimen processing to:

Roswell Park Cancer Center  
Genitourinary Malignancies Laboratory  
[name]  
Attn: [name] – I 265514  
[name]  
[name]  
[contact]  
[contact]  
[[contact]](mailto:[contact])

## 9 EFFICACY EVALUATIONS

### 9.1 Objective Tumor Response

All protocol-defined imaging studies must be performed at the investigative site or sponsor-approved facility using protocol-defined parameters. The same method of assessment and the same technique should be used to characterize each identified and reported lesion at baseline and during follow-up. RECIST 1.1 will be used to assess objective tumor response. Evaluation will be carried out for both the phase I and II study portions.

### 9.2 Target Lesions

All measurable lesions up to a maximum of 2 lesions per organ and 5 lesions in total, representative of all involved organs, will be identified as target lesions and recorded and measured at baseline. Target lesions will be selected on the basis of their size. Lesions with the longest diameter (short axis for lymph nodes) and are  $\geq 10$  mm (CT and MRI),  $\geq 15$  mm lymph nodes,  $> 20$  mm CXR and are for accurate repetitive measurements (either by imaging techniques or clinically) will be chosen. A sum of the longest diameter (short axis for lymph nodes) of all target lesions will be calculated and reported as the baseline sum diameters. This will be used as reference to further characterize the objective tumor response of the measurable dimension of the disease.

- **Complete Response (CR):** Disappearance of all target lesions. Any lymph nodes must have a reduction in short axis to  $< 10$  mm. Changes in tumor measurements must be confirmed by repeat studies performed no less than 9 weeks after the criteria for response are first met.
- **Partial Response (PR):** At least a 30% decrease in the sum of diameters of target lesions, taking as reference the baseline sum diameters. Changes in tumor measurements must be confirmed by repeat studies performed no less than 9 weeks after the criteria for response are first met.
- **Progressive Disease (PD):** At least a 20% increase in the sum of diameters of target lesions, taking as references the smallest sum on study (this includes the baseline sum if that is the smallest on study). In addition to the relative increase of 20%, the sum must also demonstrate an absolute increase of at least 5 mm. The appearance of one or more new lesions is also considered progression.

- **Stable Disease (SD):** Neither sufficient shrinkage to qualify for PR, nor sufficient increase to qualify for PD, taking as reference the smallest sum diameter while on study. Participants having a documented response with no confirmation of the response will be listed with stable disease.

### 9.3 Non-Target Lesions

All other small lesions (longest diameter < 10 mm or lymph nodes  $\geq$  10 mm to < 15 mm short axis) and non-measurable lesions (i.e., leptomeningeal disease, ascites, pleural or pericardial effusion, inflammatory breast disease, lymphangitic involvement of skin or lung, blastic bone lesions, or abdominal masses / abdominal organomegaly identified by physical exam that is not measurable by imaging) should be identified as non-target lesions and indicated as present in the source documents at baseline. The general location will also be documented on the images drawing a regularly-shaped Region of Interest. Measurements of the non-target lesions will not be performed, but the presence or absence of each should be noted throughout follow-up and evaluation.

- **Complete Response:** Disappearance of all non-target lesions and normalization of tumor marker level, if applicable. All lymph nodes must be non-pathological in size (< 10 mm short axis).
- **Non-Complete Response/Non-Progressive Disease:** Persistence of 1 or more non-target lesion(s) and/or maintenance of tumor marker level above the upper limits of normal.
- **Progressive Disease:** Appearance of 1 or more new lesions or the unequivocal progression of existing non-target lesions. Although a clear progression of non-target lesions is exceptional, in such circumstances, the opinion of the treating physician should prevail and the progression status should be confirmed at a later time.

### 9.4 Evaluation of Response

Time point response assessments will be performed every 9 weeks (timed to coincide with the end of a cycle) with a confirmatory assessment (required for non-randomized trials) within 9 weeks after a PR or CR is deemed. To determine time point response, refer to **Table 13** and below.

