| Statistical Analysis | 
Sample Size Determination: Sample size determination for the phase I portion will depend upon the dose-toxicity profile, but is expected to be between 9-18 patients. For the phase II portion, with an alpha of 0.1, assessment of 36 patients allows for a power of 0.8 to detect a minimum difference of 17% in the PFS at 18 weeks, assuming a rate of 25% under standard of care.
 
Randomization: No randomization is required.
 
Efficacy Analysis: Primary interest is in the PFS at 18 weeks after enrollment. The PFS at 18 weeks will be described by binomial proportion estimates and 90% confidence intervals. All patients in the phase II study and those treated at the RP2D in the phase I study will be included for analysis.
 
Safety Analysis: Adverse events will be tabulated. AE rates will be described using binomial proportions and 90% confidence intervals.
 
Correlative Data Analysis: Mechanistic PK/PD modeling will be employed, examining the relationship between nintedanib pharmacokinetics, modulation of CAFs and PFS.
 |
|-----------------------------|--|

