### 6.3 Criteria for Retreatment

The following criteria must be met prior to initiation of a cycle of therapy:

- ANC > 1000 / mm^3
- Platelet count > 100,000 / mm^3
- AST and/or ALT CTCAE grade ≤ 5X ULN and bilirubin ≤ ULN
- Any additional non-hematologic toxicity of grade ≥ 3 which is potentially attributable to either drug must have resolved to grade ≤ 1 (or baseline)

If a patient achieves a response or stable disease which is maintained ≥ 6 months and discontinues therapy for a reason other than progressive disease, he/she may be considered for retreatment within 3 months of cessation of therapy. This must be approved by the study PI prior to re-initiation of treatment.

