### **8.9 Schedule of Procedures and Observations**

The schedule of procedures and observations for this study is summarized in **Table 11** (Phase I) and **Table 12** (Phase II) below.

**Note:** Except for cycle 1- day 1 and day 2 procedures, *all other procedures may be performed ± 3 days from the proposed date.* Disease assessment (CT imaging) may be performed up to 7 days prior to day 1 of the corresponding cycle.

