- 6 Chemistry (complete metabolic panel (CMP): chloride, CO2, potassium, sodium, BUN, glucose, calcium, creatinine, total protein, albumin, total bilirubin, alkaline phosphatase, AST, ALT, A/G ratio, BUN/creatinine ratio, osmol (Calc), anion gap).
- 7 Pharmacokinetic samples and biomarker samples will be collected according to **Section 8.10** and **Section 8.11**, respectively.
- 8 For women of child-bearing potential only.
- 9 Baseline imaging within 4 weeks prior to treatment start. Additional scans will be taken every 9 weeks after cycle 1 –day 1 ( $\pm$  7days). CT chest + MRI abdomen/pelvis is acceptable for disease assessment, if patients are unable to undergo a contrast enhanced CT.
- 10 Medications ongoing, or stopped, within 1 week prior to first dose of study drug.
- 11 CEA is to be performed every 3 cycles from cycle 4 onward (i.e. cycle 4, 7, 10...)
- 12 Study drug reconciliation from previous cycle, prior to starting new cycle.

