#### **Sample Size Justification:**

In Phase I, using the standard 3+3 design, there will be a minimum of 9 and maximum of 18 patients enrolled.

In Phase II, the sample size calculations are based on the primary analysis of the 18-week PFS rate. Historically, the 18-week PFS rate is 5% and 25% for refractory metastatic colorectal cancer patients treated with placebo and regorafenib, respectively. The combination of nintedanib and capecitabine is expected to provide an 18-week PFS of at least 40% in patients with refractory metastatic colorectal cancer. The sample size calculation is based on testing hypotheses concerning the proportion of the treated population alive and progression free 18 weeks after enrollment. Let p represent the proportion of patients surviving with no evidence

of disease progression by RECIST at 18 weeks after start of treatment. A true PFS rate of less than  $p_0 = 0.25$  is considered unacceptable and evidence of such will deem the treatment not worthy of further study, as regorafenib has historically achieved this success rate. The null and alternative hypotheses to be tested are  $H_0: p = p_0$  versus  $H_1: p > p_0$ .

This single-stage design requires a total of 36 evaluable patients to achieve approximately  $1 - \beta$  power to detect a difference of at least  $\Delta$  percentage points ( $p_0$  versus  $p_0 + \Delta$ ). For calculations in this study,  $p_0 = 0.25$ ,  $\alpha = 0.10$ ,  $1 - \beta = 0.80$  and  $\Delta = 0.17$ . With these design parameters, the sample size was calculated using PASS v11.

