### *Primary Analysis:*

The Phase I portion of the study begins by enrolling 3 patients at Dose Level 1 (see **Table 2**). Standard 3+3 rules will be followed until the maximum tolerated (or administered) dose is found. The recommended Phase 2 dose will be considered tolerable if DLT(s) are observed in at most 1 of 6 patients completing at least 2 treatment cycles at that dose level. Available toxicity information about these drugs suggests that Dose Level 2 will be the recommended Phase 2 dose, and that 9 patients will be required for the Phase 1. The 6 Phase 1 patients treated at the recommended Phase 2 dose will be included in Stage 1 of the Phase 2 study.

The Phase 2 study's primary endpoint is the PFS rate, defined as the proportion of patients who survive without disease progression (per RECIST criteria) for least 18-weeks after the start of treatment. Patients who progress or die (due to disease or any cause) prior to 18-weeks will be counted as failures.

The following hypothesis about the true 18-week PFS rate ( $p$ ) will be evaluated using a one-sided exact binomial test:

$$H_0: p = 0.25 \text{ versus } H_1: p > 0.25.$$

If  $T = 12$  or fewer PFS responses are observed among the total  $n_1 + n_2 = 36$  evaluable patients, the therapy will be deemed ineffective; otherwise, it will be concluded that the therapy is promising. The analysis will be conducted in SAS v9.4 (Cary, NC) at a nominal significance level of  $\alpha=0.10$ .

*Secondary Analysis:* In Phase II the secondary outcomes include: overall (OS) and progression free (PFS) survival, and toxicities. A survival event is defined as a patient who experiences death from cancer or any cause, while a patient is considered censored if they are alive at the end of the

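### Scan timing and the start of the 18-week clock are each defined in two ways, so a second scan that slips past week 18 could inflate the primary PFS rate

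*Combined protocol and SAP*

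**What the plan says.** **Scan timing.** The synopsis objectives, sections 3.2.1, 3.2.2 and 4.1, and the Endpoints list in section 12 place disease assessment after every third cycle, glossed as 9 weeks. The note in section 8.9 also refers to cycles: "Disease assessment (CT imaging) may be performed up to 7 days prior to day 1 of the corresponding cycle". The synopsis procedures, section 8.3 and footnote 9 of Tables 11 and 12 use the calendar, with a window of 7 days either side; in the footnote's words, "Additional scans will be taken every 9 weeks after cycle 1 –day 1". Section 9.4 combines both: "Time point response assessments will be performed every 9 weeks (timed to coincide with the end of a cycle").

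**Delays.** Section 6.3 can hold back a cycle: "The following criteria must be met prior to initiation of a cycle of therapy". Table 10 takes patients off therapy for delays over 2 weeks, and section 6.5 allows longer ones by agreement. Section 6.1 says that an interruption within a cycle does not lengthen it.

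**Start of the clock.** The synopsis efficacy paragraph counts the 18 weeks from enrollment. Section 12.1 does so too ("alive and progression free 18 weeks after enrollment"), then defines the same proportion from start of treatment. Section 6.2 uses start of treatment, as does the primary analysis in 12.3: "for least 18-weeks after the start of treatment". For OS, the synopsis, 3.2.2 and the Endpoints list say enrollment, while the secondary analysis in 12.3 says treatment.

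**Counting.** Section 12.3 fails patients who progress or die before 18 weeks. It has no rule for a late or missing week-18 scan, and evaluable is not defined for this endpoint.

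**The concern.** The two scan schedules agree only if every cycle starts on time. Where they diverge, the patients affected are those whose next cycle was held for toxicity. If their second scan comes after week 18, progression between the first scan and week 18 is dated too late to make them failures. There is no control arm to share the error: the result is compared with a fixed 25% rate, and the exact test has little room below its nominal 0.10.

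The clock start is a separate problem that does not depend on delays. Scans are timed from the first dose, so an 18-week limit counted from enrollment can expire before the second scan is due.

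**Working it through.** **1. The plan's own figure.** Inputs from the synopsis, 12.1 and 12.3: n = 36, null rate 0.25, difference 0.17 (alternative 0.42), one-sided exact binomial test, nominal alpha 0.10, therapy promising with 13 or more successes.

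- P(X ≥ 13 | 36, 0.25) = 0.092
- P(X ≥ 13 | 36, 0.42) = 0.811

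The stated design reproduces.

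**2. When the second scan falls under the cycle wording.** Let D be the total delay in cycle starts, in weeks, up to cycle 7. Cycle 7 day 1 falls at week 18 + D. The 8.9 note allows the CT up to 7 days earlier, so the scan lies between weeks 17 + D and 18 + D.

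- D ≤ 1: a scan by week 18 is still possible.
- D > 1: it is not.
- D = 2, all before cycle 4: cycle 4 day 1 is at week 11 and cycle 7 day 1 at week 20, so the second scan is at week 19 to 20.

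**3. Status at the last scan.** Assume constant hazard (not in the documents) with 25% progression-free at week 18, so S(t) = 0.25^(t/18).

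- Delay arising after an on-time first scan: S(9) = 0.25^(1/2) = 0.500
- Two-week delay before cycle 4, first scan on cycle 4 day 1: S(11) = 0.25^(11/18) = 0.429

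**4. Effect on the test.** Let d be the share of patients whose second scan slips past week 18 and who count as successes if progression-free at the first scan. The documents give no value for d; 10% to 30% is an assumed range.

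Apparent null rate = 0.25 + d × (S(t) − 0.25); type I error = P(X ≥ 13 | 36, that rate).

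| d | Rate, last scan week 9 | Type I error | Rate, last scan week 11 | Type I error |
|---|---|---|---|---|
| 0 | 0.250 | 0.092 | 0.250 | 0.092 |
| 10% | 0.275 | 0.165 | 0.268 | 0.142 |
| 20% | 0.300 | 0.263 | 0.286 | 0.205 |
| 30% | 0.325 | 0.381 | 0.304 | 0.279 |

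On the week-9 assumption, type I error passes 0.10 at d of about 1.3%, or 0.013 × 36 = 0.5 of a patient. All entries are upper bounds for their assumptions, because they let every progression after the first scan go unseen until after week 18.

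**5. Clock start.** With a gap of g weeks from enrollment to first dose, week 18 from enrollment is week 18 − g of treatment. The earliest in-window second scan on the calendar schedule is at week 17 of treatment. If g exceeds 1, no in-window second scan precedes the enrollment-based limit. The documents do not state g.

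**The case against.** The strongest reply is that the working schedule is the calendar one. Wherever a rule with a two-sided window is given (synopsis procedures, 8.3, footnote 9), it counts weeks from cycle 1 day 1. The CT row of Tables 11 and 12 carries that footnote, so the tables cannot be cited as cycle-based just because a mark sits under cycle 4. Sections 3.2.1 and 4.1 gloss three cycles as 9 weeks. Section 6.1 keeps holds within a cycle from moving later scans, and the lead in 8.9 absorbs delays of up to 1 week. Sections 6.2 and 12.3, which define the endpoint for treatment and analysis, agree on start of treatment. All of this stands and narrows the problem: drift needs late cycle starts totalling more than 1 week and a site that follows the cycle wording. It does not remove the conflict, because nothing says which wording governs.

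Three stronger readings are tempting, and the documents do not support them.

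- A reader might infer that delayed patients reach week 18 with no scan. In the example they have had the first scan; only the second is late.
- A reader might infer that the plan counts them as successes. That is the literal consequence of the failure definition in 12.3, not a stated rule; since evaluable is undefined, they could also be excluded.
- A reader might infer that more toxicity yields a better primary result. That would need delay rates and scan practice that the documents do not give. Deaths before week 18 are still failures, and section 9.4 has symptomatic deterioration that stops treatment reported as progression. Both reduce the figures above.

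**Conclusion.** The concern holds as two contradictions in the current text, both bearing on the phase II primary endpoint, together with a missing counting rule. The possible bias favours the treatment. Its size is conditional: type I error rises from 0.092 to at most 0.142–0.165 if 10% of patients slip, 0.205–0.263 if 20% do and 0.279–0.381 if 30% do. The lower figure of each pair is for a last scan at week 11 and the higher for week 9. These rest on constant hazard, assumed slip rates, the cycle wording being followed and the literal reading of 12.3. If sites keep to the calendar schedule, the drift from cycle delays does not arise; the clock-start conflict and the missing rule remain. The ambiguity should be settled before the primary analysis.

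**What to change.** - **Scans.** In the synopsis, 3.2.1, 4.1, 8.9, 9.4 and the Endpoints list of section 12, state that scans are done every 9 weeks from cycle 1 day 1 regardless of cycle delays or dose holds, as 8.3 and footnote 9 already provide. Delete the parenthesis in 9.4 and the reference in the 8.9 note to the start of a cycle.
- **Clock.** In the synopsis, 3.2.2, the Endpoints list and 12.1, replace enrollment with cycle 1 day 1 as the origin for 18-week PFS and OS. Sections 6.2 and 12.3 already count from treatment.
- **Counting rule in 12.3.** Define week-18 status by the scan in the scheduled window of 7 days either side, so that progression on that scan is a failure even if it falls just after day 126. An on-time scan can be as late as week 19, so aligning the clocks alone does not settle this. To count as a success, a patient must have an evaluable scan, in or after that window, that shows no progression; patients without one count as failures.

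**Cost.** This is a wording amendment with no extra planned scans and no change to n = 36. Some scans will fall mid-cycle, and the observed PFS rate may be a little lower. Counting missing assessments as failures lowers power at a true rate of 0.42. If a share m of patients lack the scan regardless of outcome, power is P(X ≥ 13 | 36, 0.42 × (1 − m)): 0.734, 0.644 and 0.436 for m = 5%, 10% and 20%, against 0.811 with none missing. Sites therefore need to obtain the week-18 scan even when treatment is on hold.
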